**During a BSI** the following procedure will be done: stool collection for bacterial analysis and sIgA measurement. Extra 2 ml of blood will be collected for flagellin and LPS specific IgG levels. The blood will be obtained as soon as possible when the patient is being investigated for a suspected CA-BSI. In the event that the episode does not meet the criteria for a CA-BSI the samples will not be evaluated.

All bacterial isolates obtained during the study from patients will be saved at their respective institutions (CCHMC and University of Michigan) until the end of the study in the event further work with them is required.

**Plasma glutamine analysis:** Plasma GLN will be performed using quantitative ion exchange chromatography.

**Proinflammatory cytokine evaluation:** Analysis will be performed utilizing Luminex xMAP technology (Austin TX) as previously described.

**Measurement of Flagellin and Lipopolysaccharide- specific Immunoglobulin G level:** This will be done using enzyme-linked immunosorbent assay (ELISA) as previously described.

**Safety evaluation:** The study coordinator will contact the family by phone to assess for the development of any serious adverse events on days 15(±7 days), 45 (±7 days), 75 (±7 days), 105 (±7 days), 135 (±7 days) and 165 (±7 days). There will be a 7 day grace period before and after the desired date of safety evaluation phone calls. The phone interview will assess safety and evaluate for any symptoms suggestive of adverse side effects related to L-GLN. If hospitalized, the safety evaluation will occur with the primary caregiver (bedside nurse or parent).

**Additional safety precautions:** If while enrolled in the study the patient develops multiorgan failure or requires vasopressors, the study drug will not be administered.

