**Data collection:** During CNC/clinic visits (baseline, days 30, 60, 90, 120, 150 and 180) as described above, each child will have weight, length mid arm circumference and head circumference measured in duplicate. These measurements will be done by a trained member of the study staff at each center. The individual at each site will be trained to perform these

measurements according to standard methods previously described. Institutional scales, length boards and measuring tapes will be used at each center.

**Expected results:** We expect that SBS children on enteral GLN supplementation will have more rapid growth as measured by the parameters above. The group with no BSI or decreased BSI (2 episodes) during the study period is expected to have a greater increase in growth parameters compared to the group with > 2 BSI.

**Hypothesis 3:** The gut luminal microbiome is altered in pediatric SBS versus non-SBS controls, correlates with BSI and is altered by enteral GLN supplementation.

**Specific Aim 3:** To comprehensively assess the gut luminal microbiome (using state-of-the art molecular methods) in Aim 1 SBS patients versus non-SBS, age-matched control subjects (primary endpoint), to correlate major bacterial dynamics present in the lumen with BSI due to specific microbes and to explore whether the gut luminal microbiome is altered by enteral GLN treatment.

**Primary outcome:** Increased *K. pneumonia* and *E. faecalis* in the gut microbiome of SBS infants with BSI.

**Secondary outcome:** Alteration in other commensals in the gut luminal microbiome of SBS infants.

**Subjects:** Infants recruited in specific aim 1 (n=48 – subjects- 36; controls- 12) Healthy age matched infants (n=12) will be recruited from the Gastroenterology and surgery clinics.

**Sample Procurement:** Stool samples (~500 mcg), will be obtained from infants' diapers or ostomy bags. Stool specimens will be collected prospectively during visits at baseline, days 30, 60, 90, 120, 150 and 180. **Stool will also be collected whenever the patient has a BSI.**

The controls (12 healthy infants) will have serial stools collected on 4 occasions, each separated by 60 days (baseline, days 60, 120 and 180).

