- 8) Intestinal microbial groups (e.g., species, genera) will be correlated with the treatment or control arms of the GLN supplementation trial and with bacteria identified during any diagnosed BSI. The frequency of rRNA sequences will be interpreted as the relative abundances of organisms in samples of stool and standardized by gram of stool weight. Bacteria present in specimens will be preliminarily identified by use of the Naïve Bayesian Classifier Tool of the Ribosomal Database Project. The strength of association of individual microbial groups with treatment arms and/or main outcome measures will be measured by comparing the abundances of these groups using the non-parametric Kruskal-Wallis test. Experimental reproducibility and inter- and intra-individual similarities in microbial populations will be assessed by calculating and comparing the sequence-abundance-based Morisita-Horn index. In all statistical analyses 2-sided *p*-values less than 0.05 will be considered statistically significant. Results will be corroborated through the phylogeny-based UniFrac metric, which assesses population-wide differences in microbial lineages between different groups of subjects (SBS vs. control). Stool-associated bacteria collected at BSI incidence will be compared to the species identified on blood culture to determine whether intestinal bacteria are potential sources for BSI. Alternatively, absence of particular species from the stool at the time of BSI diagnosis will indicate that lack of specific bacterial species from the stool predisposes to BSI. Tissue samples collected during endoscopy or surgery and intestinal fluid aspirated during endoscopy will be analyzed in parallel with stool samples in order to assess the use of stool samples as proxies for intestinal samples. Patterns will also be reviewed to assess for relationships to enteral feeding rate.

These methods have been used and demonstrated in 2 published studies by one of the collaborators/co-investigators.

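### Aim 3 labels every species or genus with p below 0.05 significant without a multiplicity rule, and reads absence of a species from a stool taken during a BSI as predisposition to BSI

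*Combined protocol and SAP*

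**What the plan says.** Section XIII, Aim 3 (item 8) measures association of individual microbial groups, with species and genera given as examples, by "comparing the abundances of these groups using the non-parametric Kruskal-Wallis test". The groups are set against treatment arms and/or main outcome measures. For all Aim 3 analyses, two-sided p-"values less than 0.05 will be considered statistically significant". The number of taxa is not given, and no family-wise or false-discovery-rate rule appears anywhere in the documents.

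Section X, Specific Aim 3, makes two primary statements:
- The aim itself attaches the primary label to the microbiome "in Aim 1 SBS patients versus non-SBS, age-matched control subjects (primary endpoint").
- The separate primary outcome line is an increase in *K. pneumonia* and *E. faecalis* "in the gut microbiome of SBS infants with BSI". Other commensals are secondary.

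Section XIII does not carry this hierarchy into the testing.

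Stools are serial. For SBS infants, "Stool specimens will be collected prospectively during visits at baseline, days 30, 60, 90, 120, 150 and 180", with a further stool at each BSI. Controls "will have serial stools collected on 4 occasions, each separated by 60 days". Section XIII does not say which stool or summary enters the Kruskal-Wallis test.

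On absence, Section XIII says that not finding particular species "at the time of BSI diagnosis will indicate that lack of specific bacterial species from the stool predisposes to BSI". Section IX.H places that stool in the infection itself: during a BSI, "the following procedure will be done: stool collection for bacterial analysis and sIgA measurement".

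**The concern.** Two rules would mislead if followed exactly.

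First, an open list of taxa, each tested at 0.05 against more than one factor, will produce chance findings that carry the label of statistical significance. Aim 3 exists to link gut bacteria with BSI and with GLN, and the pilot is meant to inform a definitive study. False leads therefore have somewhere to go.

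Second, the absence sentence fixes a conclusion in advance. A species missing from the stools of infants with BSI may be just as often missing from infants without BSI. A stool taken during the infection also cannot show that the absence came first.

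A lesser gap is that the unit of analysis is not stated, although Section XIII specifies a random-effects repeated-measures model for sIgA from the same serial stools.

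**Working it through.** **The plan's own figures.** Aim 3 states no sample size or power; its only figure is the 0.05 threshold. The power statement in Section XIII belongs to Aim 1 and reproduces: exact Fisher power with 16 per arm, 75% v 30%, one-sided 10%, is 85.7% (stated as at least 85%). Nothing below changes it.

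**Inputs.** From the documents: two-sided 0.05 per test; 36 SBS infants (18 per arm) and 12 controls; 7 scheduled stools per SBS infant and 4 per control, so 36 × 7 + 12 × 4 = 300 scheduled stools from 48 infants. Assumed, because the documents give no value: 10, 20 or 50 taxa; correlation between taxa of 0, 0.3 or 0.5; correlation between stools of one infant of 0.3 to 0.7.

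**1. False taxa per contrast, all nulls true.** The expected number is 0.05 × m. The chance of at least one, for independent taxa, is 1 − 0.95^m. Correlated cases and Benjamini-Hochberg were simulated with 18 v 18 infants and one value per infant.

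| Taxa (m) | Expected false | At least one, independent | Correlation 0.3 | Correlation 0.5 |
|---|---|---|---|---|
| 10 | 0.5 | 40% | 35% | 31% |
| 20 | 1.0 | 64% | 55% | 44% |
| 50 | 2.5 | 92% | 83% | 66% |

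Under Benjamini-Hochberg at 5%, the chance of any false taxon in these settings is about 2-4%.

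The expected count does not depend on correlation between taxa, but it assumes each test has size 5%, which fails for rare taxa. With 18 v 18 and zero reads kept, a taxon present in 1 to 3 infants cannot reach p < 0.05. One present in exactly 4 does so when all 4 fall in one arm: 2 × C(18,4)/C(36,4) = 6,120/58,905 = 10.4%.

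**2. The two named taxa.** The wording is directional and joined by 'and'. If both must rise, the error is at most 5% with no adjustment. If a rise in either were enough, it would be 1 − 0.975² = 4.9% for independent taxa. A figure near 10% (1 − 0.95² = 9.75%) arises only if either taxon counts in either direction, which is not how Section X reads. The open multiplicity therefore falls on the other taxa.

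**3. The absence sentence.** No arithmetic applies. Predisposition needs the species to be absent more often in infants who go on to BSI than in those who do not, and absent before the infection. The sentence names no BSI-free stool, infant or time point, and Section IX.H collects the stool during the episode. Neither condition can be met from that stool alone.

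**4. Unit of analysis, conditional.** If every stool were entered as independent, the null error of one Kruskal-Wallis test would be 13-39% for GLN v ALA (18 × 7 v 18 × 7) and 7-29% for SBS v control (36 × 7 v 12 × 4). The low ends use a correlation of 0.3 between adjacent 30-day visits, decaying with time; the high ends use a constant 0.7. With one mean per infant the error is about 5%.

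**5. Which stools to use for SBS v control.** Averaging days 0, 60, 120 and 180 mixes on-treatment stools from GLN infants into the SBS group. With no true SBS effect and a within-infant correlation of 0.5, a GLN shift of 0.5, 1.0 or 1.5 SD makes this contrast significant in about 10%, 22% and 43% of simulated trials. The baseline stool alone gives about 5%.

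**The case against.** The strongest reply is that this is a pilot, described as exploratory, and that no decision hangs on a single taxon. The Aim 1 secondary outcomes and Aim 2 are also unadjusted. That stands as a limit on severity. It does not remove the significance label that Section XIII attaches to each taxon.

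Section XIII also has checks of its own. UniFrac is used to corroborate results, but it is a population-wide comparison of SBS with control: it controls no per-taxon error and does not address GLN v ALA or BSI. The Morisita-Horn index shows awareness of similarity within infants, but does not define the unit for Kruskal-Wallis.

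Two stronger readings are tempting. A reader might infer that the plan pools serial stools as independent observations, so that its error rates are 13-39%. The documents do not say so; they are silent on the unit, and those figures apply only if pooling were done. A reader might also infer that Aim 3 has no BSI comparator at all. That goes too far: BSI is the main outcome, and Kruskal-Wallis against main outcome measures can supply a BSI v no-BSI contrast. The absence sentence simply does not use it.

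**Conclusion.** The concern holds on two stated rules. Taxa are declared significant at 0.05 with no multiplicity control, so about 5% of those tested would be flagged by chance, with a 40%, 64% or 92% chance of at least one among 10, 20 or 50 independent taxa and less if they are correlated. The absence sentence draws a conclusion that a stool taken during the BSI cannot support without a comparator.

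The taxon counts and correlations are assumptions; that no adjustment is planned is not. The two conflicting primary statements in Section X need reconciling, and the silent unit of analysis is a point to clarify rather than a demonstrated error. Severity is minor: Aim 3 is exploratory, and the Aim 1 test and its power are untouched.

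**What to change.** (a) **Primary family and multiplicity.** Reconcile the two primary statements in Section X and carry the result into Section XIII. If the two named taxa are primary, state whether both must rise (no adjustment needed) or either suffices (Holm: 0.025, then 0.05). Apply Benjamini-Hochberg at 5% to all other taxa within each contrast and report them as hypothesis-generating.

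(b) **Absence sentence.** Delete it, or replace it with: 'Species presence and abundance in the first BSI stool will be compared with the same infant's last routine pre-BSI stool, and with the routine stool nearest in study day from SBS infants without BSI to that date. Differences are hypothesis-generating.'

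(c) **Unit, as a clarification.** Use one value per infant in each Kruskal-Wallis test:
- GLN v ALA: the post-baseline mean.
- SBS v control: the baseline stool, or later visits with alanine infants only, so that a GLN effect is not read as an SBS effect.
- BSI v no BSI: a first stool confirmed as collected before the first BSI. Section IX.H allows the first stool to be collected at home if none is obtained at the visit, so this cannot be assumed.

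**Cost.** Wording and analysis code only; every stool is already scheduled or collected at BSI. Fewer taxa will be called significant, and power is low: with one value per infant, 80% power at 0.05 needs a shift of about 1.0 SD (18 v 18 or 36 v 12 infants), and about 1.1 SD at 0.025.

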p<0.05) and enteric organisms being responsible for 62% of catheter sepsis in patients with SBS compared to only 12% in patients without SBS.

**Preliminary data strongly supports the finding of increased BSI and predominance of enteric organisms in the bloodstream of febrile SBS infants**. The SBS infants in our preliminary data also exhibit elevated levels of proinflammatory cytokines (tumor necrosis factor- $\alpha$ , interleukin 1- $\beta$ , interleukin-6 and interleukin-8) at enrollment vs. control subjects. Previous studies in adults requiring chronic home PN also showed increased blood levels of TNF- $\alpha$  and IL-6.

**Despite receiving adequate calories, SBS infants enrolled in the NICHD Neonatal Research Network had poor growth indices (length and head circumference) and also exhibited a high rate of BSI**. These findings are similar to those previously reported for SBS children requiring long term PN. Catabolic responses due to BSI and elevated systemic cytokines are likely involved in the poor growth exhibited. However, the relationship between BSI and growth failure is conjectural. There are no previous rigorous therapeutic trials designed to decrease BSI and improve growth velocity in infants affected by SBS, as we here propose.

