### **Innovation**

The available data on GLN outlined above supports the need for a rigorous, double-blind clinical study to obtain critically needed pilot data on the efficacy of enteral GLN supplementation in pediatric SBS. This proposed study represents collaborative, multidisciplinary, multisite, comparative effectiveness clinical research. The rigorous nature of this trial of GLN supplementation in SBS infants is innovative compared to previous studies; our subject group is also more homogeneous, as we limit enrollment to children with NEC, omphalocele, gastroschisis and those with atresia as the primary cause of SBS. Our proposed design incorporates important clinical outcome measures (incidence of BSI and somatic growth parameters) to provide needed information on GLN efficacy in pediatric SBS. The data, in turn, will inform the design of subsequent definitive multicenter Phase III studies. In addition, to follow-up on our studies of GLN-induced upregulation of stool and mucosal sIgA in rat models of SBS, we have measured stool sIgA in SBS children in a previous prospective trial and propose here to evaluate the impact of GLN on stool sIgA as a secondary index of enteral GLN efficacy.

**The study of the gut microbiome in pediatric SBS and the response to GLN on these microbial populations is innovative.** Commensal microbes may have a role in the immune conditioning of the gut, and may influence subsequent immune responses in neonates. The intestinal microbiome may also be important for physiologic gut absorptive and barrier functions; small bowel bacterial overgrowth and/or altered luminal microbiota (e.g. due to anatomic disruptions after intestinal resection, dysmotility, stasis, etc.) may represent a potentially crucial, but as yet uncharacterized pathophysiologic factor in SBS. The underlying disease (NEC), malnutrition, and illness-associated immunodeficiency have been hypothesized to promote the proliferation of luminal bacteria. Further, effects of altered nutrient intake in SBS on the microbiome are unknown. **Therefore, in specific aim #3, we will comprehensively assess the gut luminal microbiome in pediatric SBS patients versus controls to: 1) correlate alterations in luminal bacteria populations with BSI risk; and 2) determine whether GLN supplementation influences the gut microbiome and concomitant microbial pathogenesis of BSI.**

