**Genomic DNA Preparation:** Total genomic DNA will be prepared from specimens using a robust protocol that entails chemical and mechanical disruption of cells, which is performed in a HEPA-filtered, UV-sterilized PCR hood. Sham extractions are performed in parallel to detect contaminated reagents. **Broad-Range PCR:** DNA lysates are subjected to PCR with pan-bacterial 16S rDNA primers (27FYM+3 and 338R), yielding libraries of PCR amplicons representative of all bacteria in a specimen. Triplicate PCR reactions will be performed and amplicons pooled for each sample. To alleviate representational bias in PCR amplicon libraries, we will determine empirically the minimum number of PCR cycles required to generate the quantities of DNA required for direct sequencing by broad-range rDNA Q-PCR. **High throughput DNA Pyrosequencing:** Subject PCR amplicon libraries will be sequenced using the high-throughput Genome Sequencer™ FLX pyrosequencing platform of Roche/454 Life Sciences, Inc., available through the University of Colorado's Consortium for Comparative Genomics. Barcoded PCR primers will be used to multiplex ~200 libraries per pyrosequencer run. Approximately 5000 rRNA gene sequences will be determined for each sample library, which based on our preliminary studies will comprise a comprehensive census of the resident microbes. Additional sequences will be screened if coverage is less than 95%.

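### The Aim 3 stool-blood species comparison has no reference match rate, so it cannot separate a gut source of BSI from incidental carriage

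*Combined protocol and SAP*

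**What the plan says.** Item 8 of the Statistical Analysis Plan (Section XIII, Aim 3) says that stool bacteria collected at a BSI will be "compared to the species identified on blood culture to determine whether intestinal bacteria are potential sources for BSI". It does not give the taxonomic level of a match, a minimum abundance, a comparison stool, an expected rate or a test.

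The sentence that follows treats the opposite finding as informative too, and concludes that such a lack makes a BSI more likely: "absence of particular species from the stool at the time of BSI diagnosis will indicate that lack of specific bacterial species".

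The other analyses in item 8 address different questions:

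- Associations with treatment arm or main outcome are assessed by "comparing the abundances of these groups using the non-parametric Kruskal-Wallis test".
- Morisita-Horn and UniFrac compare whole communities.
- The general threshold, "2-sided *p*-values less than 0.05 will be considered statistically significant", is not tied to the stool-blood comparison.

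Section X sets the sequencing depth: "Approximately 5000 rRNA gene sequences will be determined for each sample library". It also names the Aim 3 primary outcome, an increase in two species (*Klebsiella* and *Enterococcus*) "in the gut microbiome of SBS infants with BSI". Section III (Innovation) gives as one purpose of the aim to "correlate alterations in luminal bacteria populations with BSI risk".

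**The concern.** A species found in both blood and stool is what one would see if the gut seeded the bloodstream. It is also what one would see if the organism came from the line or skin and the infant happened to carry the same species. The two can be told apart only by knowing how often the species turns up in stools that have no link to that infection. Item 8 asks for no such figure.

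The setting makes background matching plausible. Section III (Significance) reports "enteric organisms being responsible for 62% of catheter sepsis in patients with SBS compared to only 12% in patients without SBS", so many blood isolates will be species that live in the gut. Sequencing at the planned depth picks up trace carriage, and no abundance cut-off excludes it.

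The absence sentence adds a second problem. It draws a causal conclusion from a single stool, with no check on how often those species are absent from stools of infants without BSI.

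At stake is whether the pilot's match rate can be interpreted. The primary BSI analysis is not affected.

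**Working it through.** **Inputs from the documents**

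- 16 completers per arm; BSI rates 75% and 30% (Section XIII, Sample size).
- Enteric share of SBS catheter sepsis 62%; rate 7.8 per 1000 catheter days (Section III, Significance).
- About 5000 reads per stool; seven scheduled stools per SBS infant (Section X, Aim 3).

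**Assumptions, because the documents give no figure**

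- Carriage of an enteric blood species in an unrelated SBS stool: 30% to 90%.
- Non-enteric isolates never match.
- One BSI per affected infant in the 17-infant scenario.

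**1. The plan's own figure.** The documents state no figure for the stool-blood match. The figure that sets the expected number of infants with BSI is the power statement. Exact enumeration of the one-sided 10% Fisher test, 16 per arm, 75% versus 30%, gives 0.857, which agrees with the stated minimum of 85%.

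**2. Infants with BSI.** 16 × 0.75 + 16 × 0.30 = 16.8, taken as 17.

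**3. Detection.** A species at relative abundance *a* is seen at least once with probability 1 − (1 − *a*)^5000. At *a* = 0.06% this is 0.950; at 0.1% it is 0.993. This takes one read as detection and assumes unbiased sampling.

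**4. Chance matches when the gut is never the source.** Blood species and own stool are then independent, so P(match) = 0.62 × carriage.

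| Carriage | P(match) | Expected in 17 | P(at least one in 17) |
|---|---|---|---|
| 30% | 0.186 | 3.2 | 0.970 |
| 50% | 0.310 | 5.3 | 0.998 |
| 70% | 0.434 | 7.4 | >0.999 |
| 90% | 0.558 | 9.5 | >0.999 |

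The last column is 1 − (1 − P(match))^17.

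**5. A separate scenario counting episodes.** 36 infants × 180 catheter days (assumed) × 7.8/1000 = 50.5 episodes. Taking 50, chance matches run from 50 × 0.186 = 9.3 to 50 × 0.558 = 27.9. This is 1.4 episodes per infant (7.8 × 0.18), so repeat episodes must be expected.

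**6. What a reference rate would allow.** Exact upper-tail test at 0.025 of the match count against a known chance rate. All 17 isolates are taken here as candidates for matching, so the chance rate equals carriage.

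| Chance rate | Matches needed of 17 | Power if true match rate is 90% |
|---|---|---|
| 30% | 10 | 1.00 |
| 50% | 13 | 0.98 |
| 70% | 16 | 0.48 |
| 90% | none suffices | – |

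At 90%, 0.9^17 = 0.17, so even 17 of 17 is not significant.

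**7. Does a permutation reference behave?** Blood species were re-paired with other infants' stools in simulations in which the gut was never the source. The test rejected in 0.5% to 1.7% of runs against a nominal 2.5%. These simulations had one episode per infant, so they do not test the handling of repeats.

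**The case against.** The strongest reply is that the text claims little. It speaks only of potential sources, in an exploratory aim of a pilot, and presence in the stool is a precondition for being a source. A descriptive screen for that is not an error in itself. This stands as to tone, and the plan should not be read as declaring a proven gut source. It does not supply a comparator.

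A reader might go further in four ways that the documents do not support:

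- **That nothing could count against the Aim 3 hypothesis.** The hypothesis that the microbiome correlates with BSI has its own analysis. Abundances are compared across main outcome measures, and the Aim 3 primary outcome names two species expected to be raised in infants with BSI. A null result there would count against it.
- **That common gut species are bound to match, or that most BSIs would match by chance.** The match rate depends on carriage, which is not given. The plan sets no proportion as a threshold. If half of 17 were used for illustration, with the 62% enteric share, the chance of reaching it with no gut link is 0.2%, 5%, 14%, 29% and 69% at carriage 30%, 50%, 60%, 70% and 90%. Much higher figures arise only if every BSI is taken as enteric.
- **That concordance would be used to justify the next trial.** The Sample size section ties the future study to effect sizes and variability, and powers this one on the BSI rate.
- **That trace carriage will be scored as a match.** No match rule is stated, so the 0.06% limit shows only what is possible without a cut-off.

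Antibiotics given before the stool is collected could also lower the match rate. The documents do not fix that timing.

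**Conclusion.** The concern holds for the stool-blood comparison and for the absence sentence, and no further. As written, the comparison yields a raw match rate that cannot be told apart from background carriage, and the other item 8 analyses do not provide a reference.

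Its size is about 3 to 9.5 chance matches among 17 infants with BSI, with at least one match having probability 97% or more. These figures rest on the assumed carriage of 30% to 90%, the 62% enteric share from the cited catheter-sepsis data, no matching of non-enteric species, and the planning BSI rates.

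A reference rate improves the inference but cannot rescue it everywhere. Where carriage is near universal, species-level matching is uninformative at this sample size. A rule allowing a gut source only when matches exceed chance would then be impossible to meet, even for a species that truly came from the gut.

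This should be corrected in the SAP. It does not touch the primary endpoint.

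**What to change.** Amend item 8 as follows, using samples already scheduled:

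1. Define a match: taxonomic level and minimum relative abundance in the BSI stool.
2. For each blood species, report the observed match rate beside two references: the nearest-visit stools of other SBS infants, and the same infant's last stool before the BSI.
3. Estimate the excess over the other-infant rate, with a confidence interval, by a permutation that keeps each infant's repeat episodes together.
4. Word a match without demonstrated excess as *compatible with* a gut source. State that species-level matching is uninformative where carriage is near universal.
5. Replace the absence sentence with a comparison of those species' abundance in BSI stools against non-BSI stools.

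The cost is SAP wording, a small extra analysis and a more cautious conclusion. No new samples are needed, because each SBS infant already has seven scheduled stools.
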